#### 8.4.6.1 ECG Assessment

**Table 17. ECG Assessments Dose Escalation, 1Q3W**

Treatment Cycle	Screening	Cycles 1 and 3				Cycle 2, 4-16	Cycle 17 to PD	End of treatment	Unscheduled
Visit Number	0	1	3	4	5	1	1	-	1-X
Day/Week	≤ 21 days prior to Visit C1V1	1d	4d	8d	15d	1d	1d	-	-
Before infusion (on infusion days)	1	3	3	3	3	3	1	1	1 a
End of infusion (+15 minutes)		3							
End of infusion + 2 hours (± 15 minutes)		3							
End of infusion + 5 hours (± 30 minutes)		3							

1 = Single ECG assessment; 3= Triplicate ECG assessments

aECG assessed if relevant

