**Table 18. ECG Assessments Dose Escalation, 3Q4W**

Treatment Cycle	Screening	Cycles 1 and 3				Cycle 2, 4-12	Cycle 13 to PD	End of treatment	Unschedule d
Visit Number	0	1	3	5	6	1	1	-	1-X
Day	≤21 days prior to Visit C1V1	1d	15 d	17 d	22d	1d	1d	-	-
Before infusion (on infusion days)	1	3	3	3	3	3	1	1	1 a
End of infusion (+15 minutes)			3						
End of infusion + 2 hours (± 15 min)			3						
End of infusion + 5 hours (± 30 min)			3						

1 = Single ECG assessment; 3 = Triplicate ECG assessments

aECG assessed if relevant

Document Name: GCT1021-01 Protocol

Document Number: TMF-03326

Version: 11.0

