#### **8.4.8 Vital Signs**

Vital signs should be measured and recorded in the eCRF including temperature, blood pressure and heart rate. Vital signs will be measured as according to the schedules outlined in [Table 9](#), [Table 10](#) and [Table 11](#). Within each visit, preferably the same equipment shall be used for vital sign measurements. On infusion days, vital signs should be assessed just before and no longer than 30 minutes before infusion start, during and after the infusions until 4 hours after end of infusion of the two first infusions (dose escalation part only) and until 2 hours after the remaining infusions, as indicated in [Table 20](#), [Table 21](#) and [Table 22](#) for the dose escalation and expansion parts.

Document Name: GCT1021-01 Protocol

Document Number: TMF-03326

Version: 11.0

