**Table 20. Vital Signs during the Dose Escalation Part, 1Q3W**

Cycle 1 and cycle 2 treatment days	Cycle 3 until PD (treatment days)
Pre-infusion	Pre-infusion
15 min after start of infusion ( $\pm 5$ min)	15 min after start of infusion ( $\pm 5$ min)
At the end of infusion ( $\pm 5$ min)	At the end of infusion ( $\pm 5$ min)
15 min after end of infusion ( $\pm 5$ min)	*15 min after end of infusion ( $\pm 5$ min)
30 min after end of infusion ( $\pm 5$ min)	*30 min after end of infusion ( $\pm 5$ min)
1 hour after end of infusion ( $\pm 15$ min)	1 hour after end of infusion ( $\pm 15$ min)
4 hours after end of infusion ( $\pm 15$ min)	*2 hours after end of infusion ( $\pm 15$ min)

If infusion lasts for more than 30 minutes, vital signs should be assessed every 15 minutes ( $\pm 5$  minutes) for the remaining duration of the infusion.

\* These assessments can be skipped for the 1Q3W schedule from Cycle 7 onwards, if no infusion reaction has been observed during previous enapotamab vedotin administrations.

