## 10. STATISTICAL ANALYSIS

All statistical analysis will be performed by a Contract Research Organization (CRO) [REDACTED] under the direction of sponsor personnel. Any data analysis carried out independently by the investigator should be submitted to the sponsor prior to publication or presentation.

All data will be listed. Also, data will be summarized using descriptive statistics (continuous data) and/or contingency tables (categorical data) for demographic and baseline characteristics, efficacy measurements, safety measurements, and all relevant pharmacokinetic measurements.

The results will be presented by the 1Q3W, 3Q4W dose escalation and expansion parts separately. Also, the results will be presented by groups and total. In the dose-escalation 1Q3W and 3Q4W arms of the trial, groups are defined by dose-levels. In the expansion part, groups are defined by arm and dosing regimen. The results from the patients in the expansion part will be presented 2 times: by cohort and in total. In addition, for NSCLC patients without EGFR/ALK mutations, data will be summarized based on different dosing regimens, e.g., 1.8 mg/kg 1Q3W, 2.2 mg/kg 1Q3W. For the sake of the statistical analyses and summaries, baseline is defined as the available data from the latest recorded measurement made before the first enapotamab vedotin administration.

In general, in plots where patient data are grouped together (e.g., plots of means), the ticks on the time-axis will denote the nominal visit numbers (e.g., 0, C1V1, C1V2, C1V3 etc.) separated with distances proportionate to the difference between the time points of the corresponding visits in the relevant dose schedule (cf. the Visit Number and Day/Week rows of the assessment tables in Section 8). In plots where individual patient data are plotted vs. time, the time on the horizontal axis will denote the actual time since C1V1.

Details of statistical analysis and data reporting will be provided in a Statistical Analysis Plan (SAP) document finalized prior to database lock. Additional analyses may be added in the SAP and tables, listings and figures shells will also be provided.

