4.6 Calculated Variables

The following general definitions will be used throughout the trial:

 Baseline is defined as the latest recorded measurement made before the first IMP administration (trial day 1). Measurements done on the same date as the first IMP administration will be considered as done before the first IMP administration unless specified otherwise. For PK variables, the first IMP administration will be time 0.

TPL N°: eTPL SA-02-01 TPL Version: 02

Of SOP SA-02.08
TPL Effective Date: 31 Mar 2016
Approved in Vault: 6/30/2021

- Change from baseline is defined as the post-baseline value baseline value. Change from baseline will be missing when either post-baseline or baseline value is missing.
- Percent change from baseline is defined as 100*(post-baseline value baseline value)/baseline value. If the baseline value is 0 and the post-baseline value is 0, the change from baseline and the percent change from baseline are both 0. If the baseline value is 0 and the post-baseline value is not 0, the change from baseline is the same as the post-baseline value and the percent change from baseline will be undefined (missing).

The following variables will also be computed for the analyses described later on:

- Time (in months) from initial diagnosis of primary site to start date of IMP: (date of first IMP administration date of first diagnosis)/30.4375.
- Time (in months) since most recent recurrence/relapse or progression to start date of IMP: (date of first IMP administration – date of most recent recurrence/relapse or progression)/30.4375.
- Time (in months) since (last) biopsy to start date of IMP: (date of first IMP administration date of (most recent) biopsy before or on the start date of IMP)/30.4375. Time since biopsy will be included in the listing, time since last biopsy will be included in the biopsy table (only one result per subject).
- Time (in months) since biopsy to start date of IMP for post-baseline biopsy data: (date of (most recent) biopsy date of first IMP administration +1)/30.4375.
- Time (in months) since most recent recurrence/relapse or progression to date of most recent biopsy: (date of most recent biopsy date of most recent recurrence/relapse or progression)/30.4375.
- Time (in months) between fresh biopsy and archival biopsy (when both are available): (date of fresh biopsy date of archival biopsy)/30.4375 (only listed).
- Duration of exposure (days): (end date of IMP date of first IMP administration + 1),

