4.9 Changes to Protocol

Changes compared to protocol final version 10.0, dd. 9 December 2019:

Table 4 Evaluation of Response in section 15.1 of this SAP has been updated by clarifying the definition of not-evaluable (NE).

Subgroup analysis for Cohort 2 (up to 2 lines of prior therapy versus more than 2 lines of prior therapy within the 2.2 mg/kg dose level), Age (age<65 years and age ≥65 years), Gender, Histology: squamous versus non-squamous, ECOG performance score (0 versus 1), smoking status ((current smoker, past smoker, non-smoker), amendment 6 period (inclusion before amendment 6, after amendment 6), best response to latest regimen (CR, PR, SD, PD) and histology results (Chondrosarcoma vs other) – Cohort 5 are added.

IRC tumor assessments are not presented, the BOR and CBOR based on IRC are listed only.

PSA results (when available) and urinalysis results will only be listed.

The Safety Set is updated by removing the condition to have a valid post-baseline safety assessment as it is considered appropriate to keep all exposed subjects in the safety set to align with ICH guidelines.

Additional adverse events tables are added for completeness.

One additional analysis set is added: PK analysis set.

The interim analysis at the end of the dose-escalation part is removed as data from the dose-escalation and expansion part will be presented together as described in section 4.2.

5. Trial Subjects

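### The SAP's same-date rule makes the last first-dose-day reading the baseline: vital signs in all parts, and the +5 h ECG in 1Q3W escalation

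*SAP*

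**What the plan says.** Protocol section 10 (Statistical Analysis) states that "baseline is defined as the available data from the latest recorded measurement made before the first enapotamab vedotin administration". It has no rule for readings that share the dosing date.

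SAP 4.6 begins with an equivalent definition and then adds "Measurements done on the same date as the first IMP administration will be considered as done before the first IMP administration unless specified otherwise". The one exception given there sets time zero for PK variables. The same section defines change from baseline as the later value minus the baseline value and adds: "Change from baseline will be missing when either post-baseline or baseline value is missing".

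Two safety sections use that baseline without defining their own:
- **SAP 17.6.1 (vital signs).** Blood pressure and heart rate are notable only if an absolute limit and a change from baseline are both met.
- **SAP 17.6.3 (ECG).** QT, QTcB and QTcF changes above 30 and 60 ms, and PR and QRS changes above 25%, are tabulated. Absolute limits are reported separately for baseline and for any later visit.

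SAP 4.9 lists departures from the protocol under "Changes compared to protocol final version 10.0, dd. 9 December 2019". The same-date rule is not among them.

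**The concern.** The same-date rule is harmless for an assessment done once on the dosing day, or recorded without a time. It fails for serial readings around the first infusion. Protocol 8.4.8 requires exactly those: "On infusion days, vital signs should be assessed just before and no longer than 30 minutes before infusion start, during and after the infusions". The last Cycle 1 reading in Table 20 is "4 hours after end of infusion", and Table 17 runs 1Q3W escalation ECGs to five hours after the infusion ends.

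If every Day 1 reading counts as pre-dose and baseline is the latest of them, two things follow:
- Later changes are measured from a value taken on drug.
- No Day 1 on-drug reading is post-baseline. A QTc above 450, 480 or 500 ms at +5 h would be shown as a baseline finding, and blood-pressure or heart-rate changes around the first infusion would have no valid change from baseline.

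This is a first-in-human safety trial. Amendment 10 also dropped the plan for a separate QTc report, which leaves SAP 17.6.3 as the only QTc analysis these documents describe.

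**Working it through.** The plan gives no figure to reproduce. The check applies each baseline rule to the planned Cycle 1 Day 1 (C1D1) time points in Protocol Tables 17 to 22. The protocol rule takes the latest reading before infusion start. The SAP rule takes the latest reading dated on or before the first-dose date.

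| Assessment | Part | C1D1 time points | After infusion start | Protocol baseline | SAP baseline |
|---|---|---|---|---|---|
| ECG | 1Q3W escalation (Table 17) | 4 | 3 | pre-infusion | +5 h |
| ECG | 3Q4W escalation (Table 18) | 1 | 0 | pre-infusion | pre-infusion |
| ECG | Expansion (Table 19) | 1 | 0 | pre-infusion | pre-infusion |
| Vital signs | 1Q3W escalation (Table 20) | 7 | 6 | pre-infusion | +4 h |
| Vital signs | 3Q4W escalation (Table 21) | 7 | 6 | pre-infusion | +4 h |
| Vital signs | Expansion (Table 22) | 4 | 3 | pre-infusion | +2 h |

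The result is the same for a 0.5 h and a 4 h infusion, the protocol's minimum and maximum. In 3Q4W escalation the post-infusion ECGs fall on Day 15, so the ECG baseline there is not affected.

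**Reach.** ECG: up to 41 of about 426 subjects, 41/426 = 9.6%; at the 28 expected in that arm, 28/426 = 6.6%. Post-infusion ECGs on dosing days in Cycles 1 and 3 number 3 × 2 = 6 time points, of which 3 are on C1D1. The triplicates on Days 4, 8 and 15 remain post-baseline. Vital signs: all parts.

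**Criteria.** SAP 17.6.1 has 5 high + 5 low = 10. Systolic pressure, diastolic pressure and heart rate, high and low, give 3 × 2 = 6 that use change from baseline and have timed C1D1 readings. The two weight criteria have no reading timed around the infusion, and the two temperature criteria are absolute.

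**Hypothetical systolic pressures** (the low criterion is at most 90 mmHg with a fall of at least 20):
- Pre-infusion 112, end of infusion 88, last reading 95. From the true baseline, 88 − 112 = −24, notable. From the SAP baseline, 88 − 95 = −7, not notable, even if C1D1 readings are still checked.
- Pre-infusion 120, end of infusion 85, last reading 118. From the true baseline, 85 − 120 = −35. From the SAP baseline, 85 − 118 = −33, still at least 20. This fall is lost only if C1D1 readings are excluded as not post-baseline.

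**Illustrative QTcF shifts** (the documents give no +5 h effect). If the +5 h value exceeds the pre-dose value by s, a true later change D is reported as D − s. With D = 35 ms and s = 0, 5, 10 or 15, the reported change is 35, 30, 25 or 20 ms, and only the first exceeds 30. If true later changes were normal with mean 20 and SD 20 ms, the share above 30 ms would be 1 − Φ((30 + s − 20)/20): 31%, 23%, 16% and 7% for s = 0, 5, 10 and 20. A negative shift works the other way: D = 25 with s = −10 is reported as 25 + 10 = 35 and is flagged.

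**The case against.** The strongest reply is that the documents do not show which record was flagged. The opening sentence of SAP 4.6 points to a true pre-dose value, the same-date sentence allows exceptions, and SAP 17.6.3 names a before-infusion time point. A sensible programmer might have used it. That is fair as to what was done, but a label used for summaries is not a baseline rule, and the one sentence that addresses same-day readings says the opposite.

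Other limits stand:
- Each blood-pressure and heart-rate criterion also needs an absolute limit, so the baseline matters only for readings already past it.
- SAP 17.6.1 does not itself confine notable values to post-baseline records. That restriction comes from the change definition in SAP 4.6.
- The ECG effect is confined to one escalation arm, and a high absolute QTc at +5 h would still appear, though in the baseline column.
- Neither the direction nor the size of any bias is known.
- The protocol planned vital signs as listings only, development has stopped, and the SAP addendum repeats no ECG or vital-sign table.

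These points limit the consequence. They do not make the rule correct.

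**Conclusion.** The concern holds. As written, SAP 4.6 gives a post-infusion baseline for vital signs in every part and for ECG in 1Q3W escalation. This contradicts Protocol section 10 and is not declared. It also sits badly with SAP 4.1.1, which starts the treatment period on the first-dose date.

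The outputs at risk are:
- the notable blood-pressure and heart-rate table, and the matching flags in the vital-signs listing;
- the QT, PR and QRS categories, and the listing of subjects who meet them;
- the QTc change plot.

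Listed values, ECG summaries of actual values by time point, temperature criteria, AE tables, DLTs and the MTD are not affected.

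This assumes that the rule was programmed literally and that all C1D1 readings carry the dosing date. The time-point counts come from the protocol's schedule; the mmHg and ms examples are hypothetical.

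**What to change.** In SAP 4.6, state that for ECG and vital signs baseline is the last value at the pre-infusion time point, or clocked before the first infusion starts, using the mean of the pre-infusion triplicate for ECG measurements. State also that C1D1 readings during or after the infusion are post-baseline, and that the same-date rule applies only where neither a time nor a time-point label is recorded. List the clarification in SAP 4.9.

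Then check the baseline flag in the ECG and vital-signs datasets. The CSR was reported under SAP version 4, and the addendum reuses its definitions. If the flag used a record after infusion start, rerun Tables 14.03.21 and 14.03.23.02, Table 14.03.23.01 where it carries changes from baseline, the dependent listing flags, and the QTc change plot. That plot is described in SAP 17.6.3 but is missing from the graph list in SAP 20.2, so first confirm that it was produced.

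The cost is two sentences and a check of two datasets. No new data should be needed, provided the scheduled time points were recorded with the readings. SAP 17.6.3 reports ECGs by time point; for vital signs this needs confirming.

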#### 3.2 Trial Design Rationale

**In November 2020, Genmab decided to discontinue development of enapotamab vedotin but continue to offer treatment to patients already recruited in the present trial. In March 2021**

Document Name: GCT1021-01 Protocol

Document Number: TMF-03326

Version: 11.0

**all but 3 patients had discontinued treatment. The patients still on treatment have been on treatment for at least 7 months, which is considered sufficient time to evaluate efficacy and safety. It was therefore agreed to amend the present protocol (Amendment 10) to reduce data collection going forward. Refer to [Appendix VI](#) and [Table 31](#) for applicable procedures and assessments as of Amendment 10.**

The trial consists of a dose-escalation part with two arms (part I) and a dose expansion part (part II).

Part I of this trial is a FIH, open-label, dose-escalation, safety trial of Axl-specific ADC enapotamab vedotin in a mixed patient population with solid tumors to determine the MTD and the safety profile of enapotamab vedotin.

Part I of this trial includes two arms for identification of the most optimal dosing regimen:

- 1Q3W: Dosing once every 3 weeks.
  - There is broad experience with 1Q3W dosing of ADCs and brentuximab vedotin has received market authorization using this schedule (see Investigator's Brochure).
- 3Q4W: Weekly dosing for 3 weeks followed by one treatment-free week.

■ [REDACTED]

The less frequent dosing-arm (1Q3W) is designed as a Modified Bayesian Continuous Reassessment Method (mCRM) incorporating Escalation with Overdose Control (EWOC). This design is considered appropriate as the Bayesian mCRM in general better estimates the MTD with less bias and more precision than a classic 3+3 design. A comprehensive comparison of the Continual Reassessment Method (CRM) to the standard 3+3 dose escalation scheme in phase I dose-finding studies has been described by Iasonos et. al.

The properties of MMAE-based ADCs have been studied comprehensively and based on the overview provided by Deslandes (in particular Table 1 of the article), an U.S. Food and Drug Administration (FDA) analysis of ADCs, in combination with sponsor's own development experience with tisotumab vedotin (HuMax-TF-ADC) it is assumed that the MTD will be between 1.8 mg/kg – 2.5 mg/kg for the 1Q3W dose schedule.

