#### 8.4.7 Imaging/Computed Tomography

All patients will have a CT-scan with contrast of thorax, abdomen and pelvis performed during screening. If there is suspicion of brain metastases/tumors, a CT-scan of the head will be performed before inclusion. For patients with stable brain metastases enrolled in the expansion part, the CT-scan must include the head and neck.

For patients with superficial cutaneous lesions that are not measurable by a CT-scan, measurement using calipers can be performed, using photographs as documentation.

All sites of metastatic disease should be reported at baseline and followed throughout the trial. Up to 5 target lesions (maximum two per organ) will be defined at screening. A lesion from which a fresh biopsy has been taken during the trial cannot be a target lesion.

Baseline imaging assessments will be performed during the screening period. Any imaging assessments already completed for regular radiographic evaluation of the patient's cancer can be considered as the baseline images for this trial, as long as they are of sufficient diagnostic quality and have been obtained ≤ 28 days prior to C1D1.

Post-baseline scans will be performed every 6 weeks (1Q3W and Cohort 8 3Q4W) or 8 weeks (Cohort 6 3Q4W) (±7 days) from C1D1 until investigator assessed disease progression according to RECIST v1.1. Time points for radiographic evaluation should be calendar based and do not depend on cycle visits i.e. radiological evaluation should be performed regardless of IMP administration delays. For patients who permanently discontinue IMP for other reasons than disease progression (e.g., adverse events), every effort should be made to continue on-trial radiological evaluation according to protocol until disease progression, start of a new anti-cancer treatment, withdrawal of consent or death (see [Table 11](#)).

Document Name: GCT1021-01 Protocol

Document Number: TMF-03326

Version: 11.0

---

If reduction of target lesions  $\geq 30\%$  in size is observed a repeat CT-scan will be performed after 4 (in particular for the 3Q4W-arm) to 6 weeks (in particular for the 1Q3W-arm) to confirm the response.

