 - with end date of IMP defined as min (date of last IMP administration + 20 days, last contact date, date of death, cut-off date) For 1Q3W schedule
 - with end date of IMP defined as min (date of last IMP administration + 27 days (if D1 of cycle) or 20 days (if D8 of cycle) or 13 days (if D15 of cycle), last contact date, date of death, cut-off date) For 3Q4W schedule
- Actual cumulative dose (mg): sum of all actual doses administered.
- Planned cumulative dose (mg) only used for calculation of relative dose intensity:
 Allocated dose level * weight in kg * number of cycles initiated for 1Q3W and allocated
 dose level * weight in kg * 3 * number of cycles initiated for 3Q4W. For subjects whose
 body mass index (BMI) is greater than 30 kg/m2, the formula should use a weight
 that, based on the subject's height, corresponds to a maximum BMI of 30. When a
 cycle is missed/skipped, this cycle is also included to count the number of cycles
 initiated.
- Dose intensity (mg/cycle): actual cumulative dose in mg divided by the number of cycles initiated.
- Relative dose intensity (%): 100 * ratio of actual cumulative dose and planned cumulative dose.
- Number of days in trial: max (last contact date, date of death) date of first IMP administration + 1.

Page 13 of 46

TPL N°: eTPL SA-02-01 Of SOP SA-02.08 TPL Effective Date: 31 Mar 2016 Genmab - GCT1021-01 Version: 4.0

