17.1 Extent of Exposure

For the expansion part, the number of doses received, the duration of exposure to enapotamab vedotin (days), the actual cumulative dose (mg), as well as the actual and relative dose intensities (continuous and in categories: >= 110%, 90% to < 110%, 70% to < 90%, 50% to < 70%, < 50%, missing) will be summarized by means of descriptive statistics using the safety set.

Version: 4.0

The duration of exposure to enapotamab vedotin (days) will also be presented by a Kaplan-Meier plot (without censoring).

Also, the number of subject days (total number of days in trial) will be presented by means of descriptive statistics for each dose/cohort group.

For the dose-escalation part, only the number of doses received, number of days in the trial and the duration of exposure will be presented as mentioned above.

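### On 3Q4W, planned dose includes all three infusions of an unfinished last cycle, so relative dose intensity cannot be compared between schedules

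*SAP*

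**What the plan says.** SAP 4.6 (Calculated Variables) defines the measure in three steps.

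- Numerator: "Actual cumulative dose (mg): sum of all actual doses administered".
- Denominator: "Allocated dose level * weight in kg * number of cycles initiated for 1Q3W" and, for the weekly schedule, "dose level * weight in kg * 3 * number of cycles initiated for 3Q4W". When a "cycle is missed/skipped, this cycle is also included to count the number of cycles" initiated. Nothing is said about a last cycle that was begun but not completed.
- Result: "Relative dose intensity (%): 100 * ratio of actual cumulative dose and planned cumulative dose".

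Protocol 3.2 gives the weekly schedule: "3Q4W: Weekly dosing for 3 weeks followed by one treatment-free week". An initiated 3Q4W cycle therefore has infusions on Days 1, 8 and 15. An initiated 1Q3W cycle has one, on Day 1.

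SAP 17.1 summarises exposure for the expansion part, "as well as the actual and relative dose intensities (continuous and in categories: >= 110%, 90% to < 110%, 70% to < 90"%, followed by lower bands. SAP section 4 puts the Cohort 2 columns, Cohort 8 and the totals across each schedule on one page. SAP 4.5.2 places Cohorts 6 and 8 on 3Q4W and the other cohorts on 1Q3W.

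**The concern.** The 3Q4W denominator charges three infusions as soon as a cycle is opened. If treatment ends after Day 1 or Day 8, the remaining infusions of that cycle were never due, yet they are scored as planned and not delivered. On 1Q3W, the infusion that opens the cycle is the only one in it, so stopping cannot lower the figure. The gap arises with no dose delayed, reduced or omitted.

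Cohorts 2 and 8 enrol the same NSCLC population on the two schedules and sit side by side in the output. A reader would naturally take a lower relative dose intensity in Cohort 8 as a sign that the weekly schedule was harder to deliver. Part of any such difference would come from the definition.

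**Working it through.** The documents state no relative dose intensity (RDI) value, so there is no figure to reproduce. The check applies the SAP 4.6 formulas with full doses and constant weight. The SAP does not say which weight enters planned dose; constant weight is an assumption here.

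**Formulas.** Let c be the last cycle initiated and k (1, 2 or 3) the infusions given in it, with all earlier infusions given.

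- 3Q4W: RDI = 100 × (3(c − 1) + k) / (3c)
- 1Q3W: RDI = 100 × c / c = 100%

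**Results for 3Q4W.**

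| Last cycle | Last infusion Day 1 | Day 8 | Day 15 |
|---|---|---|---|
| 1 | 1/3 = 33.3% | 2/3 = 66.7% | 100% |
| 2 | 4/6 = 66.7% | 5/6 = 83.3% | 100% |
| 3 | 7/9 = 77.8% | 8/9 = 88.9% | 100% |
| 4 | 10/12 = 83.3% | 11/12 = 91.7% | 100% |
| 5 | 13/15 = 86.7% | 14/15 = 93.3% | 100% |
| 6 | 16/18 = 88.9% | 17/18 = 94.4% | 100% |
| 12 | 34/36 = 94.4% | 35/36 = 97.2% | 100% |

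The fully dosed 3Q4W patient is below the 90% boundary for Day 1 stops in Cycles 1 to 6 and Day 8 stops in Cycles 1 to 3. The fully dosed 1Q3W patient is never below it.

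**Scan calendar.** Protocol 8.4.7: "Post-baseline scans will be performed every 6 weeks (1Q3W and Cohort 8 3Q4W) or 8 weeks (Cohort 6 3Q4W"), within 7 days either way and independent of cycle visits.

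- Cohort 8, Day 43: 42 = 28 + 14, so this is Cycle 2 Day 15. Stopping before that infusion gives 5/6 = 83%; stopping after it gives 6/6 = 100%.
- Cohort 8, Day 85: 84 = 3 × 28, so this is Cycle 4 Day 1. Stopping before that infusion gives 9/9 = 100%; stopping after it gives 10/12 = 83%.
- Cohort 8, Day 127: 126 = 4 × 28 + 14, so this is Cycle 5 Day 15. Stopping before gives 14/15 = 93%; after, 15/15 = 100%.
- Cohort 6, Days 57, 113 and 169: all fall on Day 1 of a cycle. A patient who stops at the scan without opening the new cycle has 100%, so only stops between scans matter. If the Day 57 infusion is given before the scan is read, Cycle 3 has been opened and the value is 7/9 = 78%.
- Cohort 2: 100% at every one of its scans, whichever order applies.

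**Sensitivity to stopping times (assumed; not in the documents).** Suppose Cohort 8 patients stop only at 6-weekly scans, with probability p at each.

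- Scan read before the infusion: only Day 43 stops fall below 90%, so the share below 90% is p itself. For p = 0.4 to 0.6, mean RDI is 92% to 89%.
- Infusion given before the scan is read: only Day 85 stops fall below 90%, so the share is p(1 − p). That is 0.4 × 0.6 = 24%, 0.5 × 0.5 = 25% and 0.6 × 0.4 = 24%. Mean RDI is 95% to 96%.

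If stopping times are instead exponential with a median of 9 to 12 weeks, mean 3Q4W RDI is 87% to 89%, with 39% to 33% of patients below 90%. On 1Q3W the values are 100% and 0% in every scenario.

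**Death and cut-off.** Exposure duration in SAP 4.6 ends at the earliest of the credited end of cycle, last contact, death or cut-off. Planned dose has no such limit. A 3Q4W patient who dies on Cycle 1 Day 10 after two full infusions has 10 days of exposure but three planned infusions, so RDI is 67%.

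**The case against.** The strongest defence is that this is a deliberate, coherent convention. Exposure duration adds 27, 20 or 13 days to a last infusion on Day 1, 8 or 15, which always ends on cycle Day 28. Dose intensity is per initiated cycle. The Dose-Determining Set (SAP 4.3.4) requires three infusions in 3Q4W Cycle 1. Measuring delivery against the full planned cycle is a legitimate choice. That stands in part: there is no arithmetic error. But the exposure credit is cut off at last contact, death and data cut-off while planned dose is not, and the convention bites on one schedule only.

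The defence is also right that the measure is descriptive. No test, decision rule or formal comparison of Cohorts 2 and 8 uses it.

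Three stronger readings are tempting, and the documents do not support them.

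- A reader might infer that the scan calendar makes the loss common, with 40% to 60% of Cohort 8 below 90%. That percentage merely restates an assumed first-scan stopping rate. It also requires the Day 43 scan to be read before that day's infusion, an order the protocol does not fix.
- A reader might take 93% as the upper limit. It is only the Day 8 stop in Cycle 5; the value approaches 100% with more cycles, and treatment has no cycle cap.
- A reader might infer that early progression and poor tolerability become indistinguishable. SAP 5.1 tabulates reasons for stopping, and SAP 17.2 tabulates adverse events leading to interruption, reduction and discontinuation.

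**Conclusion.** The point holds as a comparability flaw in a descriptive exposure summary. With perfect dosing and constant weight, a 3Q4W patient who stops before Day 15 of the last initiated cycle scores between 33% and just under 100%, and a 1Q3W patient scores 100%. Early stops suffer most: every such stop in Cycles 1 to 3 falls below 90%.

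The individual values follow from the SAP formula. The effect on cohort means and category counts does not, because it depends on stopping times and on the order of scan and infusion. Under the assumptions tried, the mean shortfall in Cohort 8 ranges from about 4 to 13 percentage points. The conclusion is that the two schedules should not be compared on this measure as defined, and not that 3Q4W results are misreported by any known amount. The change is a cheap improvement and does not affect the trial's inferences.

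**What to change.** In SAP 4.6, change the 3Q4W planned cumulative dose as follows.

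- For every cycle before the last one initiated, including skipped cycles, keep three infusions.
- For the last initiated cycle, count the infusions given plus any others whose scheduled day (Day 1, 8 or 15 of that cycle) fell before the earliest of permanent discontinuation, death or data cut-off. An infusion omitted before that date still counts as planned. The SAP should name the date that represents discontinuation.

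Under this rule the fully dosed patient who stops at Day 43 scores 5/5, and the patient who dies on Cycle 1 Day 10 scores 2/2, in line with 1Q3W.

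Two wider changes should be avoided. Counting every calendar-scheduled infusion up to discontinuation could create a new asymmetry, because the protocol allows delays of up to 12 weeks and 1Q3W would still count initiated cycles. Replacing cycles by infusions in the mg/cycle dose intensity would break its unit. Leave that definition unchanged, or footnote that the last 3Q4W cycle may be incomplete.

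The cost is one SAP sentence and a small rerun of the exposure table. The SAP addendum (2.1) says the main data have already been reported under SAP version 4, so the minimum is a footnote warning against direct comparison of the schedules. The 3Q4W figures become slightly more favourable. An early stop for toxicity would no longer lower 3Q4W relative dose intensity, as is already true on 1Q3W.
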